**Analysis Plan**

---

The MG-QOL 15 total score is the sum of all 15 items. If one or more individual items are missing, the MG-QOL 15 total score will be set to missing. Note that total scores are reported on the eCRF and in general will not be recalculated.

The CFB is calculated as indicated in section 6.7.

**16.3.1.10. CFB in MG-ADL at Week 39 and Week 45**

The MG-ADL is an 8-item questionnaire. Each item grade ranges from 0 to 3. The results of the MG-ADL items are entered on the eCRF. The MG-ADL profile is shown in Appendix 5.

The MG-ADL total score is the sum of all 8 items. Higher item values represent greater severity of illness. If one or more individual items are missing, the MG-ADL total score will be set to missing. Note that total scores are reported on the eCRF and in general will not be recalculated.

The CFB is calculated as indicated in section 6.7.

**16.3.1.11. CFB in QMG at Week 39, Week 42 and Week 45**

The QMG consists of 13 individual items. The results of the QMG items are entered on the eCRF. The QMG is shown in Appendix 3.

The QMG total score is the sum of all 13 items (scored individually from 0-3) and ranges from 0 to 39. Higher item values represent greater severity of illness. If one or more individual items are missing, the QMG total score will be set to missing. Note that total scores are reported on the eCRF and in general will not be recalculated.

The CFB is calculated as indicated in section 6.7.

**16.3.1.12. CFB in MG Composite at Week 39, Week 42 and Week 45**

The MG Composite scale consists of 10 individual items. The results of the MG Composite items are entered on the eCRF. The MG Composite scale is shown in Appendix 4.

The MG Composite total score is the sum of all 10 items and ranges from 0 to 50. Higher item values represent greater severity of illness. If one or more individual items are missing, the MG Composite total score will be set to missing. Note that total scores are reported on the eCRF and in general will not be recalculated.

The CFB is calculated as indicated in section 6.7.

**16.3.1.13. CFB in Serum IgG Trough at Week 9, Week 24, and Week 39**

The CFB is calculated as indicated in section 6.7. Results from this test may include unblinding information and will be available after database lock.

**16.3.1.14. CFB in Binding, Blocking, and Modulating AChR Antibodies at Week 39**

The CFB is calculated as indicated in section 6.7. Results from this test may include unblinding information and will be available after database lock.

---

Document:

CCI

Author:

PPD

Version Number:

Final 2.0

Version Date:

12Apr2019

Template No:

CCI

Reference:

CCI

Effective Date: 01Apr2016

Copyright © 2009, 2010, 2012, 2016 CCI All rights reserved.

The contents of this document are confidential and proprietary to CCI. Unauthorized use, disclosure or reproduction is strictly prohibited.

Analysis Plan

---

16.3.1.15. CFB in HbA1c (%) at Week 39

The CFB is calculated as indicated in section 6.7.

16.3.1.16. CS-related Efficacy Variables at Week 39

The correlation between percent reduction in daily CS dose (%) at Week 39 and the following endpoints will be explored:

- CFB in systolic and diastolic blood pressure (mmHg) at Week 39
- CFB in fasting serum glucose (mg/dL) and HbA1c (%) values at Week 39
- CFB in Body weight (kg) at Week 39
- CS-related body habitus/cushingoid features at baseline and Week 39. See Section 17.4 for detailed description.
- CFB in total score of World Health Organization – Five (WHO-5) Well Being Index, which is the sum of all 5 items reported on the WHO-5 page of the eCRF, at Week 39. Each item is scored from 0 to 5 (higher scores mean better well-being). The total score, ranging from 0 to 25, are reported on the eCRF and will not be recalculated. If one or more individual scores are missing, the WHO-5 total score will be reported as missing. WHO-5 index is shown in Appendix 7.

16.3.2. MISSING DATA METHODS FOR EXPLORATORY EFFICACY VARIABLES

16.3.2.1. Missing Data Methods for Binary Endpoints

Missing values for binary endpoints will be handled using the approaches described in Section 7.3. First, the LOCF/WOCF algorithm will be used to impute the (continuous) missing values. The imputed values will then be used to derive the binary endpoints.

Note for binary endpoints related to CS dose, subjects who discontinued the study early with adverse outcomes related to MG will have their highest CS dose among all eligible visits, including the Baseline visit, carried forward to Week 39, and thus will automatically be considered as not achieving any of the following goals:

- A 75% or greater reduction in CS dose (prednisone or equivalent) at Week 39 from baseline
- CS-free at Week 39
- CS dose less than or equal to 7.5 mg per day (prednisone or equivalent) at Week 39

For subjects who have missing value due to other reasons, the missing value will be imputed using the LOCF approach as detailed in Section 7.3. The imputed LOCF values will be used to determine whether a subject achieves the goals above.

Missing data will also be handled with the OC approach, where the analysis will be based on observed

Document:	CCI	Version Number:	Final 2.0
Author:	PPD	Version Date:	12Apr2019

Template No: CCI Reference: CCI  
Effective Date: 01Apr2016

## Analysis Plan

non-missing data only and subjects with missing data at Week 39 will be excluded from the analysis.

No imputation will apply to the summary of the endpoints related to MC or episodes of MG worsening. Only OC approach will be used.

#### 16.3.2.2. Missing Data Methods for CFB Values

Missing CFB values will be handled using both the LOCF and the OC approaches described in Section 7.3. Subjects with no post-baseline values will be excluded from LOCF analysis.

Missing CFB values will also be handled using the mixed-effect model for repeated measures (MMRM) approach. The MMRM model will include CFB as the repeated dependent variable, with treatment, baseline CS dose level, protocol-specified visits, and treatment-by-visit interaction as fixed effects, with baseline value as a covariate, and with measures within-subject at each visit as a repeated measure (McCulloch, 2001). An unstructured covariance matrix will be used to model the within-subject error. If the fit of the unstructured covariance structure fails to converge, a compound symmetry covariance structure will be used. Parameters will be estimated using restricted maximum likelihood with the Kenward-Roger method for calculating the denominator degrees of freedom. For the MMRM, all available data at scheduled post-baseline visits will be utilized, including visits during follow-up phase if the data are collected. Missing data will not be imputed for MMRM.

For AChR Antibody test results, missing data will not be imputed, as this test is only scheduled at baseline and Week 39. Only OC approach will be used.

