## 7. STATISTICAL CONSIDERATIONS

### 7.1. ADJUSTMENTS FOR COVARIATES AND FACTORS TO BE INCLUDED IN ANALYSES

The following covariates and factors are used in the analyses. For details of their inclusion in the models, see the specific analysis section.

- Baseline daily CS dose (prednisone or equivalent) level (15-40 mg, 41-60 mg); as a categorical variable
- Baseline value
- Treatment group (IGIV-C, Placebo)
- Protocol specified visits (Week 0, Week 3, Week 6, Week 9, Week 12, Week 15, Week 18, Week 21, Week 24, Week 27, Week 30, Week 33, Week 36, Week 39, Week 42, Week 45)
- Treatment-by-visit interaction

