### 16.3.3. ANALYSIS OF EXPLORATORY EFFICACY VARIABLES

Exploratory efficacy analyses will be based on the mITT population. P-values presented for exploratory analyses are for information purposes only.

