## 16.3.3.2. Analysis of CFB Values

The following exploratory endpoints will be analyzed using ANCOVA model similar to the secondary endpoint in Section 16.2.3.1.

- CFB in fasting serum glucose (mg/dL) at Week 39
- CFB in MG-QOL 15 at Week 39 and Week 45
- CFB in MG-ADL at Week 39 and Week 45
- CFB in QMG Total Score at Week 39, Week 42 and Week 45
- CFB in MG Composite at Week 39, Week 42 and Week 45
- CFB in serum IgG Trough at Week 9, Week 24, and Week 39
- CFB in binding, blocking, and modulating AChR antibodies at Week 39
- CFB in HbA1c (%) at Week 39

The ANCOVA model will include CFB value as dependent variable, treatment and baseline daily CS dose level (categorical variable) as fixed factors, and baseline assessment value as covariates. Both the LOCF and OC approaches will be used to handle missing data. Treatment comparison will also be performed using the MMRM model described in Section 16.3.2.2.

Document: CCI

Author: PPD

Version Number:

Final 2.0

Version Date:

12Apr2019

Template No: CCI

Reference: CCI

Effective Date: 01Apr2016

Copyright © 2009, 2010, 2012, 2016 CCI. All rights reserved.

The contents of this document are confidential and proprietary to CCI. Unauthorized use, disclosure or reproduction is strictly prohibited.

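### The exploratory change-from-baseline MMRM uses one baseline slope for all visits, so its Week 39 contrast may be adjusted too little or too much for a chance baseline imbalance

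*SAP*

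**What the plan says.** SAP 16.3.2.2 states the response first: "The MMRM model will include CFB as the repeated dependent variable". The right-hand side of the model is then specified "with treatment, baseline CS dose level, protocol-specified visits, and treatment-by-visit interaction as fixed effects, with baseline value as a covariate". On covariance it says "An unstructured covariance matrix will be used to model the within-subject error". If that fit does not converge, "a compound symmetry covariance structure will be used". On data, "all available data at scheduled post-baseline visits will be utilized, including visits during follow-up phase if the data are collected".

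The list of model factors in SAP 7.1 contains one interaction: "Treatment-by-visit interaction". Protocol 5.1.3.3 names the MMRM but gives no terms for it. No baseline-by-visit term appears in either document.

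The protocol's Schedule of Study Procedures (Appendix 1) fixes which post-baseline visits enter:

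- QMG and MG Composite: every three weeks from Week 3 to Week 45, which is (45 − 3)/3 + 1 = 15 visits.
- MG-ADL and MG-QOL 15: Weeks 9, 24, 39 and 45.
- Fasting glucose, HbA1c and IgG: Weeks 9, 24 and 39.
- AChR antibodies: Week 39 only, so the question does not arise.

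The same endpoints also get an ANCOVA in SAP 16.3.3.2: "The ANCOVA model will include CFB value as dependent variable, treatment and baseline daily CS dose level (categorical variable) as fixed factors". It takes the endpoint's own baseline score as covariate and is run under both LOCF and observed-case handling. SAP 16.3.3 adds: "P-values presented for exploratory analyses are for information purposes only".

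**The concern.** With change from baseline as the response, the slope on baseline at a visit shows how far scores at that visit have moved away from their starting values. Nothing makes that slope constant here. Steroid dose is held through Week 6, tapered from Week 9 to Week 36, and may be raised after Week 39 (protocol 3.1 and 3.3). The MMRM lets the treatment effect and the covariance differ freely by visit, yet ties the baseline slope to one value without giving a reason.

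If the slope does change, the Week 39 treatment difference is adjusted with a pooled value. With about 30 subjects per arm, some chance baseline difference is to be expected, and part of it would stay in the contrast or be over-removed. The ANCOVA at Week 39 uses a Week 39 slope. If the two analyses differ, a reader could not tell whether missing-data handling or baseline adjustment was the cause.

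**Working it through.** **Inputs.** The visit schedules are those listed above. The documents give no SD, correlation or precision target for any of these endpoints, so there is no plan figure to reproduce on this point. The only stated sample size is for the binary primary endpoint (protocol 5.2), and it does reproduce. With 70% versus 30%, two-sided 0.05 and 80% power, n = [1.96 × √(2 × 0.5 × 0.5) + 0.842 × √(0.7 × 0.3 + 0.3 × 0.7)]² / 0.4² = 23.3, so 24 per arm; 48/0.8 = 60. It is used here only to set 30 per arm. All correlations below are assumptions.

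**Formulas** (large sample, complete data, unstructured covariance). Let b_t be the true slope of change on baseline at visit t, and S the residual covariance given baseline.

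- Common slope: c = (1′S⁻¹b)/(1′S⁻¹1).
- Part of each unit of baseline imbalance that is mis-adjusted at Week 39: c − b₃₉ (positive means under-adjusted).
- Variance ratio against a model with baseline-by-visit: 1 + (b₃₉ − c)² × var(baseline)/S₃₉. The SE ratio is its square root.

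**One case in full.** Take correlation 0.9·exp(−d/60), d in weeks, constant unit variance, 15 visits. The correlation of baseline with Week 39 is 0.9 × exp(−0.65) = 0.470, so b₃₉ = 0.470 − 1 = −0.530 and S₃₉ = 1 − 0.470² = 0.779. The common slope is c = −0.229, so the gap is 0.301. The variance ratio is 1 + 0.301²/0.779 = 1.116, and the SE rises by 5.7%. A one-standard-error chance imbalance at 30 per arm is √(2/30) = 0.258 SD. It leaves 0.258 × 0.301 = 0.078 SD in the contrast, against an effect SE of √(0.779 × 2/30) = 0.228 SD.

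**Range at constant variance** (k = number of 3-week intervals):

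| Assumed correlation | Visits | b₃₉ | c | Variance ratio | SE increase |
|---|---|---|---|---|---|
| Constant 0.6 | any | −0.400 | −0.400 | 1.000 | 0% |
| 0.9·exp(−d/60) | 15 | −0.530 | −0.229 | 1.116 | 5.7% |
| 0.9·exp(−d/100) | 15 | −0.391 | −0.180 | 1.071 | 3.5% |
| 0.85·exp(−d/60) | 15 | −0.556 | −0.290 | 1.088 | 4.3% |
| 0.8·exp(−d/80) | 15 | −0.509 | −0.315 | 1.050 | 2.5% |
| Same four | 3–4 | as above | −0.233 to −0.379 | 1.022–1.062 | 1.1–3.1% |
| 0.4 + 0.4 × 0.9^k | 15 | −0.498 | −0.335 | 1.036 | 1.8% |
| Pure autoregressive 0.97, 0.95, 0.90 per 3 weeks | 15 | −0.327, −0.487, −0.746 | −0.042, −0.082, −0.211 | 1.148, 1.222, 1.306 | 7.2%, 10.6%, 14.3% |
| Same three | 3–4 | as above | −0.110 to −0.435 | 1.083–1.119 | about 4–6% |

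**When the variance grows.** Keep 0.4 + 0.4 × 0.9^k with 15 visits, and let the score SD rise linearly from Week 9 to 1.6 times its baseline value at Week 39. Then b₃₉ = −0.197 and c = −0.269. The sign has reversed, so the model over-adjusts, with a variance ratio of 1.003. Applying the same SD growth to the four exponential settings (15 visits) gives a variance increase of only 0.1% to 0.9%, with over-adjustment in two of the four.

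**Compound-symmetry fallback.** Here c is the plain mean of the b_t, and the SE increase is 0% to 2.6% across the constant-variance patterns.

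**Finite samples.** Simulation of the four-visit schedule with 48 to 60 subjects put the SE change between about −0.7% and +2.4%. A separate simulation with 30 per arm and 20% random dropout gave SD ratios of 0.99 to 1.02 under constant and mixed patterns. Under the steep autoregressive 0.95 pattern it gave 1.05 with 4 visits and 1.08 with 15. With no true effect, the mean estimate stayed within 0.02 SD of zero in every pattern.

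**The case against.** A common baseline slope is a legitimate prespecified model, and the case for leaving it alone is substantial.

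- **Direction.** A reader might infer that Week 39 is certainly under-corrected. The documents do not support that. They give no correlations or SDs, the loss is nil if both are constant, and the sign can reverse if scores spread during the taper. Such spread is plausible, because inclusion criterion 4 admits subjects whose symptoms are controlled.
- **Bias.** A reader might also infer that the treatment estimate is biased. Under 1:1 randomisation it is not, on average. The error is conditional on the chance imbalance that occurs.
- **Scope.** It would be wrong to read the point as spanning Week 3 to Week 45 for every endpoint. That holds only for QMG and MG Composite.
- **Materiality.** Only exploratory endpoints with informational p-values use this model, and each also has an ANCOVA with its own Week 39 slope. Two complementary analyses that adjust differently do not contradict each other.
- **Cost.** For QMG and MG Composite, 14 more parameters would sit beside an unstructured matrix of 15 × 16/2 = 120, with about 60 subjects before dropout.

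All five stand as limits on the claim. They do not remove the gap. The MMRM is the only one of the planned analyses that uses incomplete subjects' data without imputation, and its one-slope restriction is neither justified nor checked.

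**Conclusion.** The point holds as a minor improvement to the plan. As written, the MMRM adjusts the Week 39 contrast with a slope pooled over unlike study periods. That may under- or over-adjust for a chance baseline imbalance and may cost some precision. The large-sample SE loss runs from 0% (constant correlation and variance) to about 6% with 15 visits and about 3% with 3–4 visits under exponential decay at constant variance. Only pure autoregressive decay takes it higher (7–14% with 15 visits, about 4–6% with 3–4). These sizes rest wholly on assumed patterns, and the 15-visit finite-sample loss is not firmly established. No conclusion on the primary or secondary endpoints depends on it.

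**What to change.** Before unblinding, amend SAP 16.3.2.2 and the factor list in SAP 7.1:

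1. Add a baseline-value-by-visit interaction to the MMRM for MG-ADL, MG-QOL 15, fasting glucose, HbA1c and IgG. This adds 3 parameters with four visits and 2 with three.
2. Add it also for QMG and MG Composite (14 parameters), provided the unstructured model converges.
3. State in advance what is dropped if it does not. One workable order is: unstructured with the interaction; then unstructured without it; then the SAP's compound-symmetry fallback with the interaction restored. Report which model was used.

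If the sponsor prefers to keep the common slope for the two 15-visit scores, a sentence of justification would do.

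The change needs no new data. If the slopes are in fact equal, it costs under 1% of the SE for the 3–4-visit endpoints. For the 15-visit models the price is some added convergence risk.

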Following a CS dose increase due to worsening MG, a second attempt at CS tapering may be made after the subject shows evidence of stabilization on the new CS dose for at least two visits (six weeks), and in the opinion of the PI, there is no contraindication to resuming the tapering. This second attempt requires that there are still visits remaining in the CS Tapering phase. Stabilization will be defined as a return to the subject's Baseline/Week 0 status prior to the episode of worsening, with QMG score ≤3 points relative to Baseline/Week 0, and return to the baseline clinical symptom(s) that initially triggered the definition of worsening of MG as judged by the physician.

On this second attempt to taper, the CS dose will be reduced in the same fashion as before; however, the dose will not decrease below the last dose at which the subject was stable prior to their episode of MG worsening. Appendix 10 provides an example of this scenario.

During the CS Tapering phase, assessments and maintenance IP infusions occur every 3 weeks. The assessments performed at the Week 9 (Visit 4) and Week 24 (Visit 9) are comprehensive and are nearly the same for both visits (with the exception that Week 24 [Visit 9] includes assessments for hemolysis and thrombosis risk); assessments at Week 12, 15, 18, 21, 27, 30, and 33 (Visits 5, 6, 7, 8, 10, 11, and 12) are identical though requiring fewer evaluations. The Week 36 (Visit 13) is the last visit which includes IP infusion and is the last time point for CS tapering.

STUDY WEEK 9 (VISIT 4)

Subjects must hold their acetylcholinesterase inhibitor (e.g., pyridostigmine) dosage for 12 hours prior to the Week 9 Visit to assure accurate assessment of the QMG score.

Additionally, subjects must fast for at least 8 hours (e.g., overnight) to allow accurate measurement of fasting serum glucose at Week 9 (Visit 4).

Assessments to be performed pre-infusion (except as specified):

- Full physical exam (excluding breast and genitourinary areas) and waist circumference. In addition, assess the following features as either absent (0) or present with grading indicated as mild (1), moderate (2), or severe (3) for each of the following:
 - a. Moon face
 - b. Centripetal obesity
 - c. Dorsalcervical fat pad
 - d. Thin skin/easy bruising
 - e. Skin striae
 - f. Hirsutism (women)
 - g. Acne (both genders)

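### Replacing a failed unstructured fit directly with compound symmetry may misstate the MMRM standard errors for QMG and MG Composite at Weeks 39 to 45, probably making them too small (minor: exploratory results only)

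*SAP*

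**What the plan says.** SAP 16.3.2.2 gives the covariance rule for the change-from-baseline endpoints. The first choice is plain: "An unstructured covariance matrix will be used to model the within-subject error". The only alternative follows: "If the fit of the unstructured covariance structure fails to converge, a compound symmetry covariance structure will be used". No intermediate structure and no empirical (sandwich) variance is named. Inference is also fixed: "Parameters will be estimated using restricted maximum likelihood with the Kenward-Roger method for calculating the denominator degrees of freedom".

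The model takes in every visit: "all available data at scheduled post-baseline visits will be utilized, including visits during follow-up phase if the data are collected". SAP 7.1 lists 16 visits from Week 0 to Week 45, of which 15 are post-baseline. The schedule in Protocol Appendix 1 collects QMG and MG Composite at all 15. MG-QOL 15 and MG-ADL have four post-baseline visits (Weeks 9, 24, 39, 45). Fasting glucose, HbA1c and IgG have three (Weeks 9, 24, 39).

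SAP 16.3.3.2 lists "CFB in QMG Total Score at Week 39, Week 42 and Week 45" and the same time points for MG Composite. ANCOVA with LOCF and with observed cases comes first, and then: "Treatment comparison will also be performed using the MMRM model described in Section 16.3.2.2".

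**The concern.** Compound symmetry assumes one variance for all visits and one correlation for all pairs of visits. It therefore applies an average variance to every visit, including the late visits that are reported. Kenward-Roger adjusts degrees of freedom and small-sample variance within the chosen structure; it cannot detect that the structure is wrong.

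There are reasons to expect the late variance to exceed the average. The model has the baseline value as a covariate. If correlation with baseline decays over 39 weeks while the raw variance stays constant, residual variance must rise. The design points the same way: Protocol 3.2.2 excludes subjects whose QMG shifts by three points between Screening and Baseline, Protocol 3.3.1 keeps the corticosteroid dose stable through the run-in, and the taper starts only at Week 9. Subjects are selected and kept stable, and are then perturbed.

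At stake are the confidence intervals and nominal p-values for QMG and MG Composite at Weeks 39, 42 and 45. A reader would use them to judge whether disease control held during the taper.

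**Working it through.** **Sample size (Protocol 5.2).** The documents state no figure for the MMRM, so the figure to reproduce is the number of subjects. With 70% against 30%, two-sided 0.05, 80% power and pooled variance, n = [1.96·√(2·0.5·0.5) + 0.8416·√(0.21 + 0.21)]²/0.40² = 23.3, so 24 per group. Allowing for 20% discontinuation, 48/0.8 = 60. Both match the protocol.

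**Covariance parameters,** v(v+1)/2:
- QMG and MG Composite: 15·16/2 = 120
- MG-QOL 15 and MG-ADL: 4·5/2 = 10
- Glucose, HbA1c and IgG: 3·4/2 = 6

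Non-convergence is a realistic risk mainly for the first pair.

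**Standard error at Week 39 under compound symmetry, complete data.** With a separate mean for each treatment at each visit, the estimate is still the Week 39 difference. Its true variance depends on v₁₃, the residual variance at the 13th post-baseline visit, but the model uses the mean of v₁ to v₁₅. Hence

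model SE / true SE = √(mean v / v₁₃), and error = 2[1 − Φ(1.96 × ratio)].

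All covariances here are assumptions. Let the raw score have unit variance, made up of a stable subject share a, a first-order autoregressive (AR(1)) share b with correlation ρ between adjacent visits, and visit noise for the rest. Then v_t = 1 − (a + bρ^t)². For a = 0, b = 1 and ρ = 0.90, mean v = 0.728 and v₁₃ = 0.935, so the ratio is √(0.728/0.935) = 0.882.

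| Assumed covariance | Ratio | Error |
|---|---|---|
| AR(1) only, ρ = 0.80 / 0.90 / 0.95 / 0.98 | 0.940 / 0.882 / 0.837 / 0.806 | 6.5 / 8.4 / 10.1 / 11.4% |
| 80% AR(1), 20% noise, ρ = 0.80 / 0.90 / 0.95 | 0.962 / 0.928 / 0.911 | 5.9 / 6.9 / 7.4% |
| 50% stable, 30% AR(1), 20% noise, ρ = 0.90 / 0.95 | 0.934 / 0.937 | 6.7 / 6.6% |
| Constant residual variance | 1.00 | 5.0% |
| Residual SD rising linearly 1.5-fold / 2-fold, Week 3 to 39 | 0.869 / 0.812 | 8.8 / 11.2% |
| Residual SD falling linearly to 0.75 / 0.5 of the Week 3 value | 1.145 / 1.46 | 2.5 / 0.4% |

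The v_t formula lets the baseline slope differ by visit, whereas the SAP model has one slope. With a common slope β equal to the mean of ρ^t, v_t = 1 + β² − 2βρ^t. For ρ = 0.90, β = 0.4765, mean v = 0.773 and v₁₃ = 0.985, a ratio of 0.886. The result barely changes.

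**Simulation.** 30 per arm, 15 visits, REML compound symmetry, 1,500 runs per setting. The critical value was fixed at 1.99 in place of Kenward-Roger, and baseline covariates were omitted.

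| Residual covariance | Complete data: ratio, error | 20% random dropout: ratio, error |
|---|---|---|
| Truly compound symmetric | 1.02, 4.6% | 1.02, 4.1% |
| Constant variance, AR(1) 0.90 | 1.00, 4.5% | 0.97, 5.7% |
| Raw AR(1) 0.90 given baseline | 0.87, 9.3% | 0.84, 9.5% |
| Raw AR(1) 0.95 given baseline | 0.84, 9.6% | 0.80, 10.4% |
| SD rising 1.5-fold | 0.87, 8.3% | 0.83, 10.7% |
| SD falling to 0.75 | 1.13, 2.8% | 1.08, 3.8% |

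Simulation agrees with the closed form. Where variance rises, dropout makes the understatement worse.

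**The case against.** A reader might infer that the plan gives standard errors that are too small. The documents do not support that as a certainty, for two reasons.

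First, the unstructured fit must fail. The comparison of 120 parameters with 60 subjects suggests risk but does not show failure: there are up to 60 × 15 = 900 observations per score. In a simulation with 30 per arm, 20% monotone dropout and 3% intermittent missingness, the unstructured fit reached a positive-definite solution in 30 of 30 runs in each of three settings. That used maximum likelihood by EM, not REML in SAS, so failure is not excluded. All the error rates above are conditional on the fallback being used.

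Second, the true variance must rise, or correlation must decay in the presence of dropout. No visit-specific SDs or correlations are given. Pure AR(1) is a steep assumption for a score built partly on timed holds and grip strength; adding visit noise moves the error towards 6 to 8%. Corticosteroid increases and withdrawals triggered by QMG worsening (Protocol 3.3.3) may also limit the late spread.

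The weight is limited too. QMG and MG Composite change are absent from the exploratory lists in Protocol 3.6.3 and SAP 2.3 and appear only in SAP 16.3. SAP 16.3.3 treats exploratory p-values as informational. ANCOVA at the same visits does not use this covariance matrix; with complete simulated data its error at Week 39 was 4.5 to 4.8%. The secondary endpoint of time to MG worsening uses a log-rank test.

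All of this stands. It lowers the severity but does not make the single-step rule a good one. SAP 7.4 says these endpoints will be presented with 95% confidence intervals, and the MMRM is the only planned analysis of these changes that uses dropouts' partial data without carrying values forward.

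**Conclusion.** The rule is a weak choice with a cheap and better replacement; severity is minor. If the fallback is reached for QMG or MG Composite, the standard errors at Weeks 39 to 45 may be misstated. Too small is the likelier direction, because variance after baseline adjustment tends to rise and the taper starts at Week 9.

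Under the assumed covariances with rising variance and complete data, the Week 39 standard error is about 4% (ratio 0.962) to 19% (ratio 0.806) too small, with a two-sided error of about 6 to 11%. Dropout can take this further. With constant residual variance and complete data the standard error is about right, and with falling variance it is too large. These figures rest on assumed correlations, not on anything in the documents, and should not be read as a forecast.

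The primary and secondary analyses do not use the MMRM. Endpoints with three or four post-baseline visits are unlikely to need the fallback.

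**What to change.** Before unblinding, replace the single step in SAP 16.3.2.2 with an ordered list and take the first structure that converges:

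1. Unstructured
2. Heterogeneous Toeplitz
3. Heterogeneous AR(1)
4. Heterogeneous compound symmetry

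Keep Kenward-Roger for these. Structures 2 to 4 let the variance differ by visit, which removes the main source of the error shown above.

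If homogeneous compound symmetry is still reached, report empirical standard errors with a small-sample correction and a stated degrees-of-freedom method, in place of Kenward-Roger. Uncorrected empirical standard errors with about 30 subjects per arm can themselves be too small, and they cannot simply be added to the Kenward-Roger method. In that case, treat the ANCOVA at the same visit as the reference result.

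The cost is slightly longer SAP text and code, and somewhat wider intervals. No data collection changes.
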